13.3.2 Goniometry

Goniometry results include measurements of knee extension, elbow extension and ankle dorsiflexion, and the results are presented as grades by side (right/left).

13.3.3 Myotools

The Myotools results will be presented as grip strength (kg) and as key pinch (kg) for the dominant hand.

13.3.4 Motor function scales

Jebson Hand Function Test (JHFT) will be presented as a total score (sec) separately for dominant and non-dominant hand. In addition, data from all subtests will be only listed (without descriptive statistics). For Performance Upper Limb (PUL) and North Star Ambulatory Assessment, total scores will be presented. Moviplate test score values will be presented separately for the dominant hand.

Motor Function Measures (MFM32 or MFM20) will be presented both separately for each dimension (D1 Standing and Transfer, D2 Axial and Proximal Motor Function, D3 Distal Motor function) and as a total score, as % of highest possible scores. In MFM32 the highest possible scores by dimension and in total are D1: 39, D2: 36, D3: 21 and Total: 96. In MFM20 the highest possible scores by dimension and in total are D1: 24, D2: 24, D3: 12 and Total: 60.

13.3.5 Timed tests

The walking distance at 1 and 2 minutes will be presented as meters. In case the subject did not complete the test, the distance at the time the test was stopped will be used for the first missing distance value for the calculation of the descriptive statistics. In this case, the time elapsed when the test was stopped will be shown in the listings.

The time to complete the 10-meter run test and the time to stand from supine will be presented as seconds. In case the subject did not complete the test, the time will be set as missing for the calculation of the descriptive statistics.

Both timed tests will be performed only for ambulatory subjects. Other reasons for not performing the test will be summarized in the listings.

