14.2.5 Vital signs

Table 14.2.5.1 Descriptive statistics of ulna length, height based on ulna length and weight

Table 14.2.5.2 Descriptive statistics of saturation of peripheral oxygen

Table 14.2.5.3 Descriptive statistics of blood pressure, heart rate, respiratory rate and body temperature

Table 14.2.5.4 Frequency distributions of being able to stand and ambulatory status

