14.3.4 Timed tests

Table 14.3.4.1 Descriptive statistics of 2 min walking test distances

Table 14.3.4.2 Descriptive statistics of 10 m run test results

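### Two-minute walk: read literally, SAP 13.3.5 gives no 2-minute value to a child who stops before 1 minute, so a shorter walk can raise the reported mean

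*SAP*

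**What the plan says.** SAP section 13.3.5 reports the walk at two time points: "The walking distance at 1 and 2 minutes will be presented as meters". If a child does not finish, the plan states for the descriptive statistics that "the distance at the time the test was stopped will be used for the first missing distance value". It adds that "the time elapsed when the test was stopped will be shown in the listings". Nothing else in the SAP text gives a rule for a second missing distance in the same test.

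Section 13 calls for absolute values and, where feasible, changes from baseline, summarised by visit. The table plan in section 18.1 contains "Table 14.3.4.1 Descriptive statistics of 2 min walking test distances". Only ambulatory children do the timed tests.

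The 10-metre and stand-from-supine tests follow a separate rule: "In case the subject did not complete the test, the time will be set as missing for the calculation of the descriptive statistics".

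**The concern.** The rule fills one value, and which value that is depends on when the child stopped. After a stop between 1 and 2 minutes, the only gap is the 2-minute distance, and it is filled. After a stop before 1 minute there are two gaps; the 1-minute distance is filled and the 2-minute distance is left with no instruction. The better of two incomplete walks then counts in the 2-minute summary and the worse one does not. The 1-minute and 2-minute rows would also rest on different children. An early stop at baseline would remove that child's 2-minute change at every later visit.

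Incomplete walks are foreseeable. The protocol synopsis admits ambulatory children only if they cannot run and need more than 5 s for 10 m, and the SAP itself provides for unfinished tests. Groups are small: the SAP describes groups of 4, with 8-12 planned at the selected dose, and the walkers are a subset of these. One child can move a mean, and a decline can show as no change. The feasibility data are meant to inform the design of later studies, so a distorted mean could mislead that use.

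**Working it through.** **Plan's own figure.** There is none. The documents give no walking distance, number of walkers, number of early stops or sample-size figure for this assessment. All distances below are assumptions. I also assume that summaries are made by dose level as well as by visit, and that stopping ends the test.

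**Step 1: apply the rule as worded.**

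| Child stops | 1-minute value | 2-minute value |
|---|---|---|
| after 2 minutes (complete) | measured | measured |
| between 1 and 2 minutes | measured | stopping distance |
| before 1 minute | stopping distance | no rule; literally missing |

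**Step 2: size for the 2-minute mean.** Take n walkers. The other n − 1 reach 100 m, and one stops before 1 minute at d metres.

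- As written: mean of the other n − 1 = 100 m.
- Stopping distance used: (100(n − 1) + d)/n.

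| n | d = 10 m | d = 25 m | d = 40 m | 100 m exceeds this by |
|---|---|---|---|---|
| 4 | 310/4 = 77.5 | 325/4 = 81.25 | 340/4 = 85.0 | 29% to 18% |
| 8 | 710/8 = 88.75 | 725/8 = 90.63 | 740/8 = 92.5 | 13% to 8% |
| 12 | 1110/12 = 92.5 | 1125/12 = 93.75 | 1140/12 = 95.0 | 8% to 5% |

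Each row treats every child in a group of that size as a walker. Since only ambulatory children are tested, 8 and 12 are upper limits for the planned 8-12 group, and a group of 4 may hold fewer than 4 walkers.

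**Step 3: the jump at 1 minute.** Four walkers, three at 100 m, and a fourth who walks 40 m per minute.

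- Completes (80 m): (300 + 80)/4 = 95.0 m, n=4.
- Stops at 61 s (40.7 m): (300 + 40.7)/4 = 85.2 m, n=4.
- Stops at 59 s (39.3 m): left out, so 300/3 = 100.0 m, n=3. With the stopping distance used it would be (300 + 39.3)/4 = 84.8 m.

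Stopping 2 s earlier raises the reported mean by 14.8 m, to above its value when the child finishes. The same jump is 29.7 m with 2 walkers, 19.8 m with 3, 7.4 m with 8 and 4.9 m with 12.

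**Step 4: change from baseline.** Same child, baseline 80 m, the others unchanged. A stop at 61 s gives (40.7 − 80)/4 = −9.8 m (n=4). A stop at 59 s gives 0 m (n=3) as written, against (39.3 − 80)/4 = −10.2 m (n=4) with the stopping distance used.

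**Step 5: direction.** If the others' mean is M, leaving the child out raises the visit mean by (M − d)/n. This is positive whenever d is below M, the likely case for a child who stops within the first minute.

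**The case against.** The strongest objection is that the SAP never says the 2-minute value stays missing; it is silent on a second missing value. A reader might infer that the plan instructs exclusion of early stoppers. It does not: the exclusion follows from a literal reading of one word, and the statistician may have meant to fill both values. That stands, and it limits the point to the wording and its literal consequence. It does not remove the point, because a programmer following the sentence exactly would fill one value.

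Second, the sizes are invented. This also stands. A reader might further infer that the visit mean would visibly rise from baseline although no child improved. That depends on who is omitted. With baselines of 120, 100, 80 and 60 m (mean 90 m) and the others unchanged, omitting the 60 m child gives 300/3 = 100 m. Omitting the 100 m child gives 260/3 = 86.7 m, and omitting the 120 m child gives 240/3 = 80 m. In each case the omitted child's decline is lost, but an apparent rise is not general.

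Third, the outcome is tertiary and descriptive, listings are the basic display, the stop time is listed, and a falling n would be a clue. All of this holds and keeps the point minor.

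Fourth, it is tempting to extend the criticism to the other timed tests and say that failures are counted in no planned table. The documents do not support that. Setting an unfinished 10-metre or stand-from-supine time to missing is acceptable for a summary of completers' times. The table plan gives titles only, such as "Table 14.3.4.2 Descriptive statistics of 10 m run test results" and "Table 14.2.5.4 Frequency distributions of being able to stand and ambulatory status", and titles do not show whether counts of missing or unable children appear inside. Nor does the absence of stand from supine from any title show that it will go untabulated. For individual children, "Other reasons for not performing the test will be summarized in the listings".

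**Conclusion.** The point holds as a flaw in the wording. Followed exactly, the sentence makes inclusion in the 2-minute summary depend on how early the child stopped, and the shorter of two incomplete walks can give the higher mean. The SAP gives no reason for accepting the stopping distance as the 2-minute result at 61 s but not at 59 s.

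Under the assumed distances, the mean with 4 walkers is too high by 15 to 22.5 m (100 − 85 and 100 − 77.5), less with 8 or 12. This rests on a literal reading, on stopping being final, and on at least one child stopping before 1 minute; otherwise the effect is zero. The documents do not show that any child did so, so nothing here says that the trial's results are distorted. The 1-minute summary, the pharmacokinetic and safety analyses and the dose decisions are untouched. It is worth considering, not essential.

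**What to change.** Reword the sentence in section 13.3.5 so that the distance at stopping is used for every later missing time point, at 1 and at 2 minutes, given that stopping ends the test. Flag those values in the listing. If the test allows rest and resumption, which the protocol synopsis does not say, state that and use the distance actually reached. If filling both values was already the intention, the new wording simply records it. Because the SAP's introduction says that its authors and reviewers had access to the study data, label the change as made after data access.

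The cost is one sentence and a small programming change, using a distance the present rule already needs. The downside is that every stop is treated as final, including stops for reasons other than ability; the listed stop time lets a reader see when the child stopped.

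Optional, and not the correction of an error: since feasibility is the tertiary objective, show the numbers tested, completed and unable beside the timed-test summaries, as far as the collected data distinguish them. Such counts may already be planned. Completers' times for the other tests can stay as they are.

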Study Endpoints	
• The Primary Endpoint is the pharmacokinetic profile of omigapil and metabolites quantified by C_{max}, C_{min}, t_{max}, $t_{1/2}$, AUC_{0-t}, AUC_{0-8h}, AUC_{0-24h}, λ_z (terminal phase rate constant) and R_o (the extent of accumulation in plasma)• The Secondary Endpoint is safety and tolerability of omigapil at the doses tested, established through the collection of Adverse Events (AEs) and Serious Adverse Events (SAEs), vital signs, oxygen saturation, standard lab parameters and electrocardiogram (ECG) assessments.• The Tertiary Endpoint is the outcome of disease-relevant clinical assessments.
• Hospital-based pulmonary function tests (PFTs) by standard spirometry.• Home-based pulmonary function tests using a child-compatible hand-held device (ASMA-1).• Hospital-based evaluation of muscle strength & function.• Motor function scales.

- Time tests (ambulatory patients only).
- Functional Scales.
- Muscle Imaging (Muscle magnetic resonance imaging (MRI) and Muscle Ultrasound)
- Collection of biomarkers

Number of Centers

1

Number of Subjects
Patient Population

Approximately 20 eligible patients will be randomly assigned to ensure a minimum of 16 patients who have completed all study procedures (3 cohorts of 4, 4, and 8-12 patients)

Inclusion Criteria

- Ambulatory and non-ambulatory patients from age 5 - 16 years (≥ 5 years old and < 17 years old) at time of screening with a clinical picture (see below) consistent with COL6-related dystrophy (COL6-RD) or LAMA2-related dystrophy (LAMA2-RD)
- Under regular review at a neuromuscular center
- On adequate double-barrier contraception (if of child-bearing potential (CBP))
- Stable on any allowed concomitant medications for 1 month prior to run in phase
- Forced Vital Capacity (FVC) 30-80% of the predicted value and confirmed at Screening and Baseline visit(s)

For patients with Collagen VI-related dystrophy (COL6-RD)– required clinical picture

- Muscle weakness: inability to walk or, if patient is still ambulatory, inability to run and > 5 s for 10 m walk

Genetics and Pathology:

- Molecular diagnosis of COL6-RD, defined by one dominant or two recessive mutation(s) in COL6A1, COL6A2 or COL6A3 known to cause the clinical picture,
OR

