- Histological diagnosis showing (i) absent or significantly decreased expression of collagen VI in muscle (overall reduction or basal lamina specific) or (ii) absent or significantly abnormal matrix in skin fibroblast culture

For patients with Laminin alpha 2 related dystrophy (LAMA2-RD) – required clinical picture

- Muscle weakness: Inability to walk; if patient is still ambulatory, inability to run and > 5 s for 10 m walk.

Genetics and Pathology:

- Either: 2 identified pathologic or probable pathologic mutations in LAMA2 gene
OR
- 1 identified pathologic or probable pathologic mutation in LAMA 2 gene with evidence of decrease in laminin alpha 2 staining on muscle or skin biopsy

OR

- Evidence of decrease in laminin alpha 2 staining on muscle or skin biopsy with matching clinical phenotype and no suspicion of alpha dystroglycanopathy (aDG-RD) (clinically or by staining on muscle biopsy)

Exclusion Criteria

- Use of any investigational drug other than the study medication within 12 weeks of study start.
- Recurrent hospitalization for chest infections in previous 2 years (≥ 2 per year)
- Patients with respiratory parameters (eg: low pulmonary function test value i.e. $<30\%$ predicted or need for daytime non-invasive ventilation) currently affected by short term medications, or acute illness/ conditions (conduct baseline assessments when the patient has recovered and is no longer taking acute medication)
- Any need for surgery (i.e. scoliosis, gastrostomy, other) in the preceding 24 weeks or foreseen during the course of the study.
- Patient has an intercurrent significant medical condition or situation which in the opinion of the Investigator or the study Medical Monitor may put the patient at significant risk, confound the study results or interfere significantly with the patient's participation in the study.
- Failure to thrive, defined as:
 - Falling 20 percentiles (20/100) in body weight in the 12 weeks preceding Screening/Baseline (based on family report of weight loss and review of relevant medical records)
 - In patients below the 3rd percentile, any further drop in body weight percentile in the 12 weeks preceding Screening/Baseline (based on family report of weight loss and review of relevant medical records)
- Weight less than 17 kg at Baseline
- Morbidly obese or grossly overweight (≥ 86 percentile body mass index (BMI) in children)
- History of epilepsy or on antiepileptic medication at Screening/Baseline
- Diabetes

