Safety Evaluations	
• Physical examination, vital signs including body temperature, ECG, pulse oximetry, laboratory assessments such as complete blood cell counts (CBC), comprehensive metabolic panel (CMP), liver ultrasound, urine analysis and AE collection
Efficacy Evaluations	
Feasibility
 
• Hospital-based pulmonary function tests by standard spirometry: Forced Vital Capacity (FVC), Slow Vital Capacity (SVC), Forced Expiratory Volume (FEV1), Peak Expiratory Flow (PEF), Maximum Inspiratory Mouth Pressures (MIP), Maximum Expiratory Mouth Pressures (MEP), Peak Cough Flow (PCF) and Sniff Nasal Inspiratory Pressure (SNIP).• Home-based pulmonary function tests using a child-compatible hand-held device (ASMA-1): PEF and FEV1• Hospital-based hand-held myometry: elbow flexion, elbow extension, knee flexion, knee extension, myotools/Moviplate

- Hospital-based goniometry: knee extension/flexion contracture, elbow flexion contracture, ankle dorsiflexion
- Hospital-based Timed tests: 2 minute walk and 10 meter walk
- Hospital-based motor function scales: North Star, MFM 32, Performance Upper Limb (PUL) scale, Jebsen Hand Function Test
- Hospital-based functional Tests: ACTIVLIM, Egen Klassifikation (EK2)
- Muscle imaging (muscle ultrasound and muscle MRI)

Study Procedures

16-20 CMD patients (8-10 COL6-RD and 8-10 LAMA2-RD) whose weight, age, and FVC likely meet the inclusion/exclusion criteria will be notified of the study. Patients may be identified using known data from the annual Congenital Muscular Dystrophy natural history study (CMD Comparative Outcome Measure Study- CMD COM) at the NIH or through the CMDIR. Trial flyers will be distributed through an outreach organization Cure CMD as well as through other community contacts. Patients who have learned of the trial by any means, including clinicaltrials.gov and flyer distribution, may contact the investigators directly and be considered for screening.

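### The SAP summarises a 10 m run where the protocol synopsis specifies a 10 m walk and excludes ambulatory children who can run; setting non-completers to missing biases the reported times towards faster values

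*SAP*

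**What the plan says.** **The test.** The protocol synopsis, under Efficacy Evaluations, lists "Hospital-based Timed tests: 2 minute walk and 10 meter walk". SAP 13.3.5 names a different 10 m test and adds a rise from supine: "The time to complete the 10-meter run test and the time to stand from supine will be presented as seconds". The table plan in SAP Appendix 18.1 repeats the name: "Table 14.3.4.2 Descriptive statistics of 10 m run test results".

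**Who can be tested.** SAP 13.3.5 says "Both timed tests will be performed only for ambulatory subjects", and the synopsis also limits the timed tests to ambulatory patients. To be eligible, COL6-RD patients must show "inability to walk or, if patient is still ambulatory, inability to run and > 5 s for 10 m walk". The LAMA2-RD criterion is equivalent: "Inability to walk; if patient is still ambulatory, inability to run and > 5 s for 10 m walk".

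**Non-completion.** For the 10 m test and the rise from supine, SAP 13.3.5 states: "In case the subject did not complete the test, the time will be set as missing for the calculation of the descriptive statistics". For the timed walking distance the same section does the opposite and uses the distance reached when the test stopped. Reasons for not performing a test go to the listings.

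**Declared changes.** SAP section 14 covers only the decision not to run a per-protocol analysis.

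**The concern.** There are two linked problems.

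1. The test cannot be identified. A 10 m run is planned for children whose eligibility rests on being unable to run. If a run was really attempted, the table should be almost empty. If a walk was timed, the table is mislabelled. If children were told to go as fast as they could, the result need not be comparable with the walk time used at entry. The tertiary objective is to inform the design of later studies, and a reader planning one needs to know which test was feasible.

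2. Failing to finish carries information about ability. A still-ambulatory child who could do the test at baseline and later cannot has shown the largest worsening that the test can register. Under the missing rule that child leaves both the visit mean and the change from baseline. Because longer times are worse, removing the slowest child makes the group look faster. The planned tables show no count of children who tried and could not, although for a feasibility objective that count is a main result.

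**Working it through.** The documents give no completion rate, number of ambulatory children or expected time for these tests, so there is no planned figure to reproduce. The check is a comparison of texts followed by an illustration of direction.

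**Step 1: the texts side by side**

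| Item | Protocol synopsis | SAP |
|---|---|---|
| 10 m test | Walk | Run (13.3.5 and Table 14.3.4.2) |
| Entry, ambulatory children | Unable to run, and more than 5 s for a 10 m walk | Not restated |
| Rise from supine | Not in the timed-test list | In 13.3.5; no table title in Appendix 18.1 names it |
| Difference declared | – | Not in section 14 |

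The SAP uses the word run in both the text and the table plan, so it is not a single slip.

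**Step 2: how many records survive**

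Let m be the number of ambulatory children at a dose level and q the chance of not completing; both are assumptions. Expected records kept = m(1 − q). Chance of at least one missing value = 1 − (1 − q)^m. The planned cohorts are 4, 4 and 8–12 patients, ambulatory or not, so m = 4 is the maximum for a planned cohort of 4.

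| q | Kept, m = 4 | Kept, m = 8 |
|---|---|---|
| 0 | 4 | 8 |
| 0.25 | 3 | 6 |
| 0.50 | 2 | 4 |
| 0.75 | 1 | 2 |
| 1 | 0 | 0 |

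At q = 0.25 the chance of at least one missing value is 1 − 0.75^4 = 68% for m = 4 and 1 − 0.75^8 = 90% for m = 8. A literal run puts q near 1. A walk may put it near 0.

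**Step 3: direction of the bias**

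Assume four children with baseline times of 8, 10, 14 and 20 s. At follow-up the first three take 8.5, 11 and 15 s, and the fourth cannot complete. All four are worse.

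| Summary | Baseline | Follow-up | Appears |
|---|---|---|---|
| Mean time, SAP rule | 52/4 = 13.0 s | 34.5/3 = 11.5 s | 12% better |
| Median time, SAP rule | 12 s | 11 s | better |
| Mean change, three completers | – | (0.5 + 1 + 1)/3 = +0.83 s | worse, fourth child omitted |
| Mean velocity (10/time), 0 if unable | (1.250 + 1.000 + 0.714 + 0.500)/4 = 0.87 m/s | (1.176 + 0.909 + 0.667 + 0)/4 = 0.69 m/s | 21% worse |
| Median time, unable ranked worst | 12 s | (11 + 15)/2 = 13 s | worse |

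The SAP's absolute summaries move the wrong way. Its change from baseline moves the right way but leaves out the child who worsened most. Both summaries that keep the fourth child show the decline.

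**The case against.** The strongest case on the other side has five parts.

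- **Loss of ambulation is not hidden.** SAP 12.3 summarises ability to stand and ambulatory status by visit and dose level, and Table 14.2.5.4 gives their frequencies. Ambulatory status also appears in the listings of clinical assessments. This stands. A reader might infer that losing the ability to walk is recorded as no data at all, and that is not so. What the tables miss is narrower: the child who is still ambulatory but fails the 10 m test or the rise.
- **Change from baseline is also planned, where feasible.** This stands. In the illustration it shows +0.83 s, so the reader would not see improvement alone. It still excludes the non-completer.
- **Nothing shows that only the ablest children remain.** This stands. A reader might infer it from the missing rule, but the documents give no completion rate. A literal run would leave almost nobody, while a walk might keep nearly everyone. What can be said is that the summary is restricted to completers.
- **The SAP may have the right name.** Only the protocol synopsis was available for this review, and the SAP authors had access to study data, so run may describe what was recorded. This stands against simply substituting walk. It does not remove the need to reconcile the two documents.
- **The stakes are low.** The assessment is tertiary and descriptive, dose determination rests on AUC, and with so few children the individual listings carry much of the information. This stands, and it limits the weight of the point.

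**Conclusion.** The point holds in a limited form. The SAP and the protocol synopsis name different 10 m tests, the SAP's version conflicts with the entry criterion for every ambulatory child, and the difference is not declared. Setting non-completers to missing restricts the 10 m and supine statistics to completers and biases them towards faster times. SAP 13.3.5 itself retains partial information for the walking distance.

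The size cannot be derived from the documents. The illustration (13.0 to 11.5 s, against 0.87 to 0.69 m/s) rests on assumed times and one assumed failure and shows direction only. The actual effect depends on how many children were ambulatory, which test they did and how many failed it.

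The documents do not support concluding that the walk is necessarily the test that was performed. Nor do they support concluding that a dose decision or a primary or secondary result is affected. The consequence is confined to the tertiary feasibility summaries, and the correction is cheap enough to be worth making.

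**What to change.** 1. Confirm from the CRF which 10 m test was done and what instruction the child was given. Use that name in SAP 13.3.5 and Table 14.3.4.2. If it differs from the protocol's walk, declare this in SAP section 14.
2. For the 10 m test and the rise from supine, tabulate the numbers attempted, completed and unable by visit and dose level. Give the rise from supine its own table title, and state in section 14 if it is an addition to the protocol.
3. Add one summary that keeps inability: velocity (10/time), or 1/time for the rise, with 0 for unable; or a median with unable ranked worst. Include children no longer tested because ambulation was lost. The worst-rank median cannot be given as a time once half or more are unable, so velocity is the more robust choice in groups of about four.
4. Reserve missing for reasons unrelated to ability.

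The cost is SAP wording and simple programming, since reasons for not performing the test are already to be listed. The drawback is that velocity is less familiar than seconds, so the times in seconds should stay in the listing.
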